13.3 Time Period and Frequency for Event Assessment and Follow-Up

The occurrence of an adverse event (AE) or serious adverse event (SAE) may come to the attention of study personnel during study visits and interviews of a study participant presenting for medical care or upon review of the medical record.

Adverse events will be recorded with start dates occurring any time after informed consent is obtained until 7 (for non-serious AEs) or up to 30 days (for SAEs) after the 6 month visit. At each study visit, the investigator will inquire about the occurrence of AE/SAEs since the last visit. Events will be followed for outcome information until adequate resolution or stabilization.

All AEs including local and systemic reactions not meeting the criteria for SAEs will be captured on the appropriate case report form (CRF). Information to be collected includes event description, time of onset, clinician's assessment of severity, relationship to study product (assessed only by those with the training and authority to make a diagnosis), and time of resolution/stabilization of the event. All AEs occurring while on study must be documented appropriately regardless of relationship. All AEs will be followed to adequate resolution.

Any medical condition that is present at the time that the participant is screened will be considered as baseline and not reported as an AE. However, if the study participant's condition deteriorates at any time during the study, it will be recorded as an AE.

Changes in the severity of an AE will be documented to allow an assessment of the duration of the event at each level of severity to be performed. AEs characterized as intermittent require documentation of onset and duration of each episode.

13.4 REPORTING ADVERSE EVENTS

Adverse events will be recorded from the time of informed consent and for 30 days after the 6 month visit regardless of whether or not the event(s) are considered related to the study procedure. All AEs considered related to study procedures will be followed until resolution, return to baseline, or deemed clinically insignificant, even if this is after the 6 month visit Any death occurring within 30 days after intervention must be reported as an SAE regardless of attribution.

13.4.1 Reporting to the IRB

Unanticipated problems involving risks to subjects or others will be reported promptly to the IRB if they:

- 1. are unexpected;
- 2. are related or possibly related to participation in the research; and
- 3. suggest that the research places subjects or others at a greater risk of harm than was previously known or recognized.

If the serious adverse event does not meet all three (3) criteria listed above, the event does not have to be promptly reported to the Indiana University IRB. However, it should be reported at the time of continuing review.

Prompt reporting of unanticipated problems to the IRB is defined **as within 5 days** from becoming aware of the event.

13.4.2 Reporting the IUSCC Data Safety Monitoring Committee

Regardless of study sponsorship, the study team must enter all initial and follow-up SAE, expedited, and noncompliance reports into OnCore® for review by the DSMC chair and/or coordinator. Expedited reports may include IRB Prompt Report Forms and additional SAE forms as required by the sponsor. When follow-up information is received, a follow-up report should also be created in OnCore®. This DSMC reporting requirement is in addition to any other regulatory bodies to be notified (i.e. IRB, FDA, pharmaceutical company, etc.). The DSMC chair and/or coordinator will review all SAE, expedited, and noncompliance reports monthly and findings will be reported to the full DSMC quarterly. See section 14.5 for additional details

14.0 DATA SAFETY MONITORING PLAN

This study will be conducted in accordance with the IU Simon Cancer Center Institutional DSMP for Moderate Risk Trials.

Investigators will conduct continuous review of data and subject safety. Monthly review meetings for moderate risk trials are required and will include the principal investigator, clinical research specialist/coordinator and/or research nurse (other members per principal investigator's discretion). Monthly meeting summaries should include review of data, the number of subjects, significant toxicities as described in the protocol, and responses observed. Study teams should maintain meeting minutes and attendance for submission to the DSMC upon request.

14.1 Data and Safety Monitoring Committee

The IUSCC Data and Safety Monitoring Committee (DSMC) is responsible for oversight of subject safety, regulatory compliance, and data integrity for this trial. The DSMC will review this study annually to review overall trial progress, toxicity, compliance, data integrity, and accrual per the Institutional DSMP.

Furthermore, the DSMC conducts an administrative review of serious adverse events (SAEs), deviations, reportable events, and any other outstanding business. Major issues may require further DSMC review or action.

For any increase in frequency of grade 3 or above adverse events (above the rate reported in the Investigator Brochure or package insert), the principal investigator will notify the DSMC Chair immediately. The notification will include the incidence of study adverse events, grades, and attributions, as well as investigator statements regarding comparison with risks per the IB/ package insert.

At any time during the conduct of the trial, if it is the opinion of the investigators that the risks (or benefits) to the subject warrant early closure of the study, the DSMC Chair and Compliance Officer must be notified within 1 business day via email, and the IRB must be notified within 5 business days. Alternatively, the DSMC may initiate suspension or early closure of the study based on its review.

14.2 Study Auditing and Monitoring

All trials conducted at the IUSCC are subject to auditing and/or monitoring per the Institutional DSMP. Reports will be reviewed by the full DSMC at the time of study review.

14.3 Data Management/ Oncore Reporting Requirements

The DSMC will review data and study progress directly from Oncore and REDCap; therefore, timely data entry and status updates are vital. Study data must be entered promptly, no later than one week from study visit occurrence. Subject status in Oncore will be updated in real time, as this may affect overall trial enrollment status. Global SAEs and deviations will be reviewed on a monthly basis by the DSMC Chair directly from Oncore.

14.4 Study Accrual Oversight

Accrual data will be entered into the IU Simon Cancer Center OnCore system. The Protocol Progress Committee (PPC) reviews study accrual twice per year, while the PPC coordinator reviews accrual quarterly.

14.5 Oncore Safety Reporting

In addition to protocol- and regulatory-required safety reporting, all serious adverse events (SAEs) will be captured in the Oncore system within 1 business day of notification. Initial SAE reporting will include as much detail as available, with follow-up to provide complete information. Attributions will be assessed to study drugs, procedures, study disease, and other alternate etiology.

14.6 Protocol Deviation Reporting

Protocol deviations will be entered into OnCore within 5 days of discovery and reviewed by the DSMC Chair on a monthly basis. Findings will be reported to the full DSMC at the time of study review. For serious or repetitive protocol deviations, additional action may be required by the DSMC.

16.0 Appendices

- 16.1 Appendix I Protocol Amendment History
- 16.2 Appendix II COST FACIT Questionnaire
- 16.3 Appendix III FACT-G Questionnaire
- 16.4 Appendix IV mRECIST Criteria
- 16.5 Appendix V CTCAE Version 5.0 Criteria
- 16.6Appendix VI Screen Fail Form
- 16.7 Appendix VII SBRT Constraints

16.1 Appendix I Protocol Amendment History

The table below is intended to capture changes of IRB-approved versions of the protocol, including a description of the change and rationale. A Summary of Changes table for the current amendment is located in the Protocol Title Page.

Version	Date	Description of Change	Brief Rationale

16.2 Appendix II COST FACIT Version 1

Confidential

COST FACIT Version I

Study ID		_			
Below is a list of statements to Please mark one answer per	-	•		•	
	Not at all	A little bit	Somewhat	Quite a bit	Very much
I know that I have enough	\bigcirc	\circ	() 		
assets to cover the costs of my treatment			mone	ey in savings, reti	rement, or
My out-of-pocket medical	\bigcirc	\bigcirc	\bigcirc	\bigcirc	
thought they would be	Ü	expe	nses are more tha	an I	
I worry about the financial problems I will have in the future as a result of my illness or treatment	0	0	0	0	
I feel I have no choice about the	\bigcirc	\bigcirc	\bigcirc	\bigcirc	
care	Ü	Ü	amount of m	oney I spend on	
I am frustrated that I cannot work or contribute as much as I usually do	0	0	0	0	
I am satisfied with my current	\circ	\bigcirc	\bigcirc	\bigcirc	
0			financial si	tuation	
I am able to meet my monthly	0	\circ	expenses	\circ	
I feel financially stressed	\bigcirc	\bigcirc	\bigcirc	\circ	\bigcirc
I am concerned about keeping	\bigcirc	\bigcirc	\bigcirc	\bigcirc	
work at home			my	job and income,	including
My cancer or treatment has or present financial situation	0	reduce	O ed my satisfaction	o with my	
I feel in control of my financial situation	\bigcirc	0	0	0	

projectredcap.org

16.3 Appendix III FACT-G Version 4

FACT-G (Version 4)

Study ID	
Below is a list of statements that other people Please choose one number per line to indicate	le with your illness have said are important. te your response as it applies to the past 7 days.
PHYSICAL WELL-BEING	
I have a lack of energy	0 - Not at all 1 - A little bit 2 - Somewhat 3 - Quite a bit 4 - Very much
I have nausea	 0 - Not at all 1 - A little bit 2 - Somewhat 3 - Quite a bit 4 - Very much
Because of my physical condition, I have trouble meeting the needs of my family	 0 - Not at all 1 - A little bit 2 - Somewhat 3 - Quite a bit 4 - Very much
I have pain	 0 - Not at all 1 - A little bit 2 - Somewhat 3 - Quite a bit 4 - Very much
I am bothered by side effects of treatment	 0 - Not at all 1 - A little bit 2 - Somewhat 3 - Quite a bit 4 - Very much
I feel ill	 0 - Not at all 1 - A little bit 2 - Somewhat 3 - Quite a bit 4 - Very much
I am forced to spend time in bed	 0 - Not at all 1 - A little bit 2 - Somewhat 3 - Quite a bit 4 - Very much

SOCIAL/FAMILY WELL-BEING	
I feel close to my friends	 0 - Not at all 1 - A little bit 2 - Somewhat 3 - Quite a bit 4 - Very much
I get emotional support from my family	 0 - Not at all 1 - A little bit 2 - Somewhat 3 - Quite a bit 4 - Very much
I get support from my friends	0 - Not at all 1 - A little bit 2 - Somewhat 3 - Quite a bit 4 - Very much
My family has accepted my illness	 0 - Not at all 1 - A little bit 2 - Somewhat 3 - Quite a bit 4 - Very much
I am satisfied with family communication about my illness	 0 - Not at all 1 - A little bit 2 - Somewhat 3 - Quite a bit 4 - Very much
I feel close to my partner (or the person who is my main support)	0 - Not at all 1 - A little bit 2 - Somewhat 3 - Quite a bit 4 - Very much
Regardless of your current level of sexual activity, please answer the following question.	I prefer not to answer
I am satisfied with my sex life	0 - Not at all 1 - A little bit 2 - Somewhat 3 - Quite a bit 4 - Very much
Please choose one number per line to indicate	e your response as it applies to the past 7 days.
I feel sad	0 - Not at all 1 - A little bit 2 - Somewhat 3 - Quite a bit 4 - Very much

I am satisfied with how I am coping with my illness	 0 - Not at all 1 - A little bit 2 - Somewhat 3 - Quite a bit 4 - Very much
I am losing hope in the fight against my illness	 0 - Not at all 1 - A little bit 2 - Somewhat 3 - Quite a bit 4 - Very much
I feel nervous	 0 - Not at all 1 - A little bit 2 - Somewhat 3 - Quite a bit 4 - Very much
I worry about dying	 0 - Not at all 1 - A little bit 2 - Somewhat 3 - Quite a bit 4 - Very much
I worry that my condition will get worse	 0 - Not at all 1 - A little bit 2 - Somewhat 3 - Quite a bit 4 - Very much
FUNCTIONAL WELL-BEING	
I am able to work (include work at home)	0 - Not at all 1 - A little bit 2 - Somewhat 3 - Quite a bit 4 - Very much
My work (include work at home) is fulfilling	0 - Not at all 1 - A little bit 2 - Somewhat 3 - Quite a bit 4 - Very much
I am able to enjoy life	 0 - Not at all 1 - A little bit 2 - Somewhat 3 - Quite a bit 4 - Very much
I have accepted my illness	 0 - Not at all 1 - A little bit 2 - Somewhat 3 - Quite a bit 4 - Very much

I am sleeping well	 0 - Not at all 1 - A little bit 2 - Somewhat 3 - Quite a bit 4 - Very much
I am enjoying the things I usually do for fun	0 - Not at all 1 - A little bit 2 - Somewhat 3 - Quite a bit 4 - Very much
I am content with the quality of my life right now	0 - Not at all 1 - A little bit 2 - Somewhat 3 - Quite a bit 4 - Very much

Copyright © 2010 FACIT.org

16.4 Appendix IV Modified (mRECIST) Criteria Assessment for Hepatocellular Carcinoma

An electronic copy of the mRECIST critieria can be found at the following website: https://imaging.cancer.gov/clinical_trials/docs/mRECIST%20for%20HCC%202010.pdf

16.7 Appendix VII: SBRT Constraints

Desired SBRT Constraints:

Structure	Volume	Dose / Constraint
PTV	>95%	Rx
GTV	>98%	>110% Rx
Liver – GTV	700cc or V10 Gy	<1500cGy or <70%
	1/3 uninvolved	<1000cGy (CTP-A), <1800cGy (CTP-B7)
	500cc uninvolved	<700cGy (CTP-A), <1200cGy (CTP-B7)
Duodenum	0.5 cc	2400 cGy (3 fraction) 3000 cGy (5 fraction)
	<5 cc	1650 cGy (3 fraction) 1800 cGy (5 fraction)
	<10 cc	1140 cGy (3 fraction) 1250 cGy (5 fraction)
Stomach	0.5 cc	2250 cGy (3 fraction) 3000 cGy (5 fraction)
Esophagus	0.5 cc	32 Gy (5 fx)
Spinal Cord	100%	<600cGy/fraction
Chest Wall	100%	<5000cGy
	<5cc	4000cGy
	<30cc	3000cGy
R Kidney	2/3	<2000cGy
L kidney	1/3	<1500cGy
Heart	0.5 cc	3000 cGy (3 fraction) 5250 cGy (5 fraction)

Variation acceptable Constraints (per RTOG 1112)

Structure	Variation acceptable	Deviation unacceptable
Esophagus max (0.5 cc)	>32 but ≤34 Gy	>34 Gy
Stomach max (0.5 cc)	>30 but ≤32 Gy	>32 Gy
Duodenum max (0.5 cc)	>30 but ≤32 Gy	>32 Gy
Small bowel max (0.5 cc)	>30 but ≤32 Gy	>32 Gy
Large bowel max (0.5 cc)	>32 but ≤34 Gy	>34 Gy
Spinal cord + 5 mm max (0.5 cc)	>25 but ≤28 Gy	>28 Gy
Kidneys: bilateral mean	>10 but ≤12 Gy	>12 Gy

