7.0 STUDY INTERVENTION

7.1 Study Interventions

There are two comparative intervention arms, both of which are currently standard-of-care.

7.1.1 Selective transarterial radioembolization (Radiation Segmentectomy (RS)):

This therapy arm involves two separate steps, a planning/mapping arteriogram and a therapy delivery. The planning arteriogram will be performed to confirm arterial anatomy is acceptable for RS (\leq 2 segment delivery) and that lung shunting is not too high to preclude treatment with RS. Once confirmed, patients will return for RS (within 45 days of mapping). Dose will be calculated based off the desired treatment volume using pre-treatment cross-sectional imaging. The desired segmental dose will be calculated to be \geq 200Gy. RS will be performed by one of three separate interventional radiologists with experience in radioembolization. Actual administered activity and location of dose administration will be recorded.

7.1.2 Stereotactic Body Radiation Therapy (SBRT):

SBRT will be delivered with linear accelerator-based photon beams with either fixed angle non-coplanar fields or dynamic arcs. For treatment planning, CT simulation with triple phase IV contrast would be performed in the treatment position (supine, arms up). Tumor motion management would be assessed with 4D CT through the breathing cycle. Abdominal compression or breath-hold may be used at physician discretion for diaphragmatic excursion of 1cm or more. Available pre-treatment diagnostic imaging will be fused with the planning CT by deformable registration to assist in target and normal tissue delineation. An internal target volume (ITV) will be generated to account for tumor movement during breathing cycle. Finally, a planning target volume (PTV) will be an expansion of 3-5mm from the ITV. For Child Pugh A patients, prescription dose will either be 5000cGy in 5 fractions delivered every other day or 4800cGy in 3 fractions delivered twice weekly. For Child Pugh B patients, prescription dose of 4000cGy in 5 fractions delivered every other day. Inverse planning will be used. 95% of the PTV or more will receive at least 100% of the prescription dose. Normal tissue dose constraints for each dose level will be respected with acceptable deviations permitted as outlined in appendix VII. Patients will be seen at least once per week by a clinician to grade toxicities, with on- treatment labs (CBC, CMP, INR) each week.

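### Appendix VII's acceptable-variation table does not say that it is for 5-fraction plans only, although section 7.1.2 also allows 48 Gy in 3 fractions

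*Combined protocol and SAP*

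**What the plan says.** Section 7.1.2 gives Child-Pugh A patients one of two SBRT prescriptions: 50 Gy in 5 fractions, or "4800cGy in 3 fractions delivered twice weekly". Footnote C of the Schedule of Events repeats this choice. Child-Pugh B patients receive 40 Gy in 5 fractions only. On organ doses, section 7.1.2 states: "Normal tissue dose constraints for each dose level will be respected with acceptable deviations permitted as outlined in appendix VII".

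Appendix VII (section 16.7) has two tables.

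- **Desired constraints.** Six rows name a schedule: three for duodenum and one each for stomach, esophagus and heart. At 0.5 cc, duodenum reads "2400 cGy (3 fraction) 3000 cGy (5 fraction", stomach "2250 cGy (3 fraction) 3000 cGy (5 fraction" and heart "3000 cGy (3 fraction) 5250 cGy (5 fraction". The esophagus row gives 32 Gy and is marked for 5 fractions only. Small and large bowel have no row.
- **Acceptable variation.** The heading is "Variation acceptable Constraints (per RTOG 1112". None of its seven rows names a schedule. Duodenum and stomach are acceptable above 30 and up to 32 Gy, and esophagus above 32 and up to 34 Gy. This table also has the rows "Small bowel max (0.5 cc" and "Large bowel max (0.5 cc", the only place where those two organs appear.

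**The concern.** The desired table treats the number of fractions as decisive for the upper gastrointestinal organs: the duodenum and stomach limits are lower in 3 fractions than in 5. The table that decides which excesses are tolerable then drops the distinction. Because section 7.1.2 refers every dose level to this appendix, a planner working in 3 fractions has to decide whether the variation bands apply.

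At stake is the dose to duodenum and stomach in individual patients. A planner or auditor who takes the table at face value could pass a 3-fraction plan well above the appendix's own 3-fraction limit. One who takes it as a 5-fraction table would reject the same plan.

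**Working it through.** **Inputs.** All are 0.5 cc limits from the two tables of Appendix VII, with cGy divided by 100.

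| Organ | Desired, 3 fractions | Desired, 5 fractions | Variation band |
|---|---|---|---|
| Duodenum | 24 Gy | 30 Gy | >30 to 32 Gy |
| Stomach | 22.5 Gy | 30 Gy | >30 to 32 Gy |
| Esophagus | none given | 32 Gy | >32 to 34 Gy |

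**Step 1: which schedule do the bands extend?** The lower edges of the bands are 30, 30 and 32 Gy. Each equals the 5-fraction desired limit exactly, and neither available 3-fraction limit matches. For 5 fractions the two tables join without a gap, and the tolerance is 32/30 − 1 = 6.7% for duodenum and stomach and 34/32 − 1 = 6.25% for esophagus.

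**Step 2: the table applied literally to 3 fractions.**

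- Duodenum: 30/24 − 1 = 25% and 32/24 − 1 = 33% above the desired limit.
- Stomach: 30/22.5 − 1 = 33% and 32/22.5 − 1 = 42% above the desired limit.
- Dose per fraction at the top of the band: 32/3 = 10.7 Gy. The desired limits correspond to 24/3 = 8.0 Gy (duodenum) and 22.5/3 = 7.5 Gy (stomach). The same 32 Gy in 5 fractions is 32/5 = 6.4 Gy.

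**Step 3: the table taken as 5-fraction only.** Duodenum and stomach keep their 3-fraction limits of 24 and 22.5 Gy with no tolerance, so the excesses in step 2 do not arise. What remains is that three organs have no 3-fraction limit: esophagus, whose desired limit is marked for 5 fractions, and small and large bowel, which appear only in the variation table.

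Steps 2 and 3 are alternatives, and their results should not be added together.

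**Step 4: reach.** Section 10.3 allows up to 10 patients per arm, and the replacement rule in section 10.4 adds patients only to the radioembolization arm. Child-Pugh B patients never receive 3 fractions. The documents do not say how many Child-Pugh A patients will. The range is therefore 0 to 10.

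**The case against.** The strongest reply is that nobody would read the table literally. The bands begin exactly where the 5-fraction limits end, explicit 3-fraction limits stand a few lines above, and section 7.1.2 requires the limits of each dose level to be kept. A literal reading would also be incoherent: it would accept 31 Gy to the duodenum in 3 fractions while listing no tolerance for 27 Gy. Most of this stands. The 5-fraction reading is the more natural one, and the step 2 figures describe a misreading that the text permits, not an intended dose.

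The heading's reference to an outside protocol may also fix the fractionation. That cannot be checked from these documents. If it does, it confirms the 5-fraction reading, and the label is still missing from the page that a planner uses.

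Three fractions is optional as well: any Child-Pugh A patient may be planned in 5, and the synopsis allows dose to be adjusted for safety. This lowers the practical consequence but does not tell a 3-fraction planner which rule applies.

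Two stronger inferences should be resisted.

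- A reader might infer that 3-fraction doses between the desired limit and 30 Gy (24 to 30 Gy for duodenum, 22.5 to 30 Gy for stomach) are left unclassified. Section 7.1.2 permits only the deviations that the appendix sets out, so an excess with no listed band is better read as not permitted.
- A reader might infer that the protocol authorizes 32 Gy to these organs in 3 fractions. It does not say so. It only fails to rule it out in the table.

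**Conclusion.** The point holds as a minor planning-safety correction. The variation table should state its schedule. Without that, its wording would accept 30 to 32 Gy to duodenum or stomach in 3 fractions, against the appendix's own limits of 24 and 22.5 Gy. The conclusion rests only on the two tables and on section 7.1.2, and it needs no radiobiological assumption.

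The absence of 3-fraction limits for esophagus and bowel is a secondary matter of missing detail and does not carry the point by itself.

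A reader might infer some effect on the trial's results, since toxicity of grade 4 or higher is compared between arms. The documents do not support that. Dosimetric class enters neither the analysis population in section 10.4 nor any planned test, and the primary endpoint is recruitment and screen failure. No statistical figure changes.

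**What to change.** 1. Label the Appendix VII variation table as applying to 5-fraction plans only.
2. Add one sentence: in 3-fraction plans the desired 0.5 cc limits of 24 Gy (duodenum) and 22.5 Gy (stomach) are binding, with no acceptable variation.
3. As a secondary step, have radiation oncology either add 3-fraction limits for esophagus, small bowel and large bowel, or require the 5-fraction schedule when one of these organs lies near the target. The values cannot be derived from the documents.

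A general rule that the stricter of the two tables governs should not be added. Each duodenum, stomach and esophagus band is looser than its desired limit (32 against 30 Gy for duodenum, 34 against 32 Gy for esophagus), so the rule would cancel those bands for 5-fraction plans too.

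The cost is one label, one sentence and a short radiation-oncology review. Visits, sample size and analyses stay as they are.

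### Appendix VII heart row: the 5-fraction limit (5250 cGy) allows more dose per fraction than the 3-fraction limit (3000 cGy), so the two values do not fit together

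*Combined protocol and SAP*

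**What the plan says.** The table of desired constraints in Appendix VII (section 16.7) gives the heart limit for 0.5 cc as "3000 cGy (3 fraction) 5250 cGy (5 fraction". Four other rows also print a pair of limits:

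- duodenum 0.5 cc: "2400 cGy (3 fraction) 3000 cGy (5 fraction"
- duodenum <5 cc: "1650 cGy (3 fraction) 1800 cGy (5 fraction"
- duodenum <10 cc: "1140 cGy (3 fraction) 1250 cGy (5 fraction"
- stomach 0.5 cc: "2250 cGy (3 fraction) 3000 cGy (5 fraction"

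The spinal cord row is written per fraction (below 600 cGy each). The same table asks for more than 98% of the GTV to receive more than 110% of the prescription.

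Section 7.1.2 sets the schedules. The Child-Pugh A group has two options: "prescription dose will either be 5000cGy in 5 fractions delivered every other day or 4800cGy in 3 fractions delivered twice weekly". The other group has a single schedule at a lower dose: "For Child Pugh B patients, prescription dose of 4000cGy in 5 fractions delivered every other day". On the status of the limits, the section says: "Normal tissue dose constraints for each dose level will be respected with acceptable deviations permitted as outlined in appendix VII". The second table in Appendix VII, which lists acceptable variations, has entries for stomach and duodenum but none for heart. No reason or source is given for either heart value.

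**The concern.** When a course is split into more fractions, the total limit for an organ may rise, but one would not expect the dose allowed at each fraction to rise as well. In the heart row it does. A 5-fraction plan that meets its own limit has already passed the 3-fraction limit by its third fraction.

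This row is the protocol's only limit on heart dose. A Child-Pugh A patient may receive either schedule, and no rule for choosing between them is stated, so the choice of five fractions raises the permitted heart dose by 75% without explanation. Child-Pugh B patients receive only a 5-fraction schedule, at a prescription well below the heart limit. For a tumour close to the heart, a plan could pass the check as written while giving a small volume of heart the full prescribed dose.

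**Working it through.** The protocol states the limits without deriving them, so there is no calculation of its own to reproduce. The check takes the totals in Appendix VII and assumes equal fractions, in line with the fixed schedules in section 7.1.2.

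**Step 1: dose per fraction.** Total limit divided by number of fractions. **Step 2: dose after three of five fractions.** 3 × (5-fraction limit / 5), compared with the 3-fraction limit. **Step 3: increase in total limit.** 5-fraction limit / 3-fraction limit − 1. For the cord, the totals follow from the per-fraction limit: 3 × 6 = 18 Gy and 5 × 6 = 30 Gy.

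| Row | Limit, 3 fr (Gy) | Limit, 5 fr (Gy) | Gy per fraction, 3 → 5 | Three of five fr (Gy) | As % of 3-fr limit | Increase in total |
|---|---|---|---|---|---|---|
| Heart 0.5 cc | 30 | 52.5 | 10.0 → 10.5 | 31.5 | 105% | 75% |
| Duodenum 0.5 cc | 24 | 30 | 8.0 → 6.0 | 18.0 | 75% | 25% |
| Duodenum <5 cc | 16.5 | 18 | 5.5 → 3.6 | 10.8 | 65% | 9% |
| Duodenum <10 cc | 11.4 | 12.5 | 3.8 → 2.5 | 7.5 | 66% | 10% |
| Stomach 0.5 cc | 22.5 | 30 | 7.5 → 6.0 | 18.0 | 80% | 33% |
| Spinal cord | 18 | 30 | 6.0 → 6.0 | 18.0 | 100% | 67% |

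Heart is the only row above 100%. At its limit, a 5-fraction plan still has 52.5 − 31.5 = 21 Gy to give. The schedules do not explain this: five fractions are given every other day and three are given twice weekly, so the first three fractions of the longer course are not more widely spaced.

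**Step 4: highest 5-fraction value compatible with 30 Gy in 3.** 5 × 30/3 = 50 Gy. At exactly 5000 cGy, three fractions give 30 Gy and meet the 3-fraction limit.

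**Step 5: heart limit against prescription and GTV goal.**

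- 50 Gy in 5: 52.5/50 = 105%. The GTV goal is above 1.10 × 50 = 55 Gy, which exceeds the heart limit.
- 40 Gy in 5: 52.5/40 = 131%. The GTV goal is above 1.10 × 40 = 44 Gy, which is below the heart limit.
- 48 Gy in 3: 30/48 = 62.5%.

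**Step 6: guide from the paired rows.** Applying the smallest and largest duodenum and stomach increases to 30 Gy gives 30 × 18/16.5 = 32.7 Gy and 30 × 30/22.5 = 40.0 Gy, or about 3270 to 4000 cGy.

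**The case against.** The strongest reply is that 5250 cGy is not a tissue tolerance but a cap on hot spots, since it is exactly 105% of the 50 Gy prescription. With a GTV goal above 55 Gy in that regimen, such a cap does restrict dose in heart next to the target. This reading is plausible, but the table does not state it. The row would then combine a limit at 62.5% of prescription (three fractions) with one at 105% (five fractions), and the cap would not work at 40 Gy, where it lies above the GTV goal.

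It can also be said that these are desired constraints, that a cautious 3-fraction goal and a looser 5-fraction ceiling can coexist, and that no patient is subject to both. The table's heading does support a softer status. But section 7.1.2 commits the team to respecting the constraints, and the variation table offers no fallback for heart.

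A reader might infer three stronger conclusions that the documents do not support:

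- **That the 5-fraction value is shown to be wrong.** The arithmetic shows only that the pair is inconsistent.
- **That the linear-quadratic model fixes the correct value.** Assuming that model without a time factor, the 5-fraction equivalent of 30 Gy in 3 is at most 30 × √(5/3) = 38.7 Gy. The cord row fails the same test (18 × √(5/3) = 23.2 Gy against 30 Gy, 29% over), and stomach is 3% over. The table is not built on equal effect, so the model cannot single out heart or supply its limit.
- **That any limit above a prescription dose is an error.** The chest wall limit of 5000 cGy also exceeds the 40 Gy prescription. The fault lies in the mismatch within the heart row.

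**Conclusion.** The inconsistency stands. The 5-fraction heart limit allows 10.5 Gy per fraction against 10.0 Gy for three fractions and passes the 3-fraction limit after fraction 3 (31.5 against 30 Gy). This rests on the printed values and equal fractions, and needs no radiobiological model.

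The 5-fraction value is the likelier error, because it exceeds both 5-fraction prescriptions and its 75% step is larger than in any other row (9% to 67%). That is a judgement, and the source of the constraints would settle it. In practice the limit binds somewhat in the 50 Gy regimen and hardly at all in the 40 Gy Child-Pugh B regimen.

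The point concerns treatment-planning safety. It reaches at most 10 SBRT patients (section 10.3), and among them only those with tumours near the heart. The feasibility endpoint is unaffected.

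**What to change.** Radiation oncology should check both heart values against the source they were taken from and amend the row.

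- If 3000 cGy in 3 fractions stands, the 5-fraction limit should not exceed 5000 cGy (10 Gy per fraction). A lower value in line with the duodenum and stomach rows, about 3270 to 4000 cGy, is a guide only. The cord pattern of constant dose per fraction would allow up to 5000 cGy.
- If 5250 cGy is meant as a 105% hot-spot cap for the 50 Gy regimen, label it so and give the 40 Gy regimen its own limit of no more than 1.05 × 40 = 42 Gy (4200 cGy). Such caps still let 0.5 cc of heart receive the full prescription dose, and the amendment should say whether that is intended.

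The cost is one row in an amendment and one clinical check. A few plans for tumours near the heart may lose a little target coverage.
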